#### 10.3.6.2. Assessment

#### **Description**

If the event consists of a cluster of signs and symptoms, a diagnosis should be recorded (e.g. gastroenteritis) rather than each sign and symptom.

#### Onset and end

The dates and times of the onset and end of the event should be recorded.

#### **Assessment**

#### **Challenge Virus Symptoms**

The Investigator will assess and review Challenge Virus related symptoms recorded in participants' hVIVO Symptom Diary Cards. Symptoms greater than Grade 0 will be expected and presumed to represent virus infection consequent to Viral Challenge, and will not be additionally captured as AEs unless they meet the definition of an AE, and are deemed to be clinically significant (in the opinion of the Investigator) to be classed as AEs.

Following Viral Challenge all unexpected (in the opinion of the Investigator) symptoms post inoculation will be captured as AEs, along with all other occurrences that meet the criteria for an AE.

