#### 2.3. Benefit/Risk Assessment

More detailed information about the known and expected benefits and risks and reasonably expected adverse events of Palivizumab may be found in SmPC; although possible. Side effects of Palivizumab have been established in paediatric population at high risk of severe RSV infection following an intramuscular

hVIVO template identifier: (G\_0687) v3.0

(IM) administration of Palivizumab. Historical studies in 48 healthy adults (CDER\_FDA 2004) using liquid and lyophilised Palivizumab administered as both Intramuscular (IM) and IV injections have reported no serious adverse events (SAEs). The most common side effect observed in adults was mild transient dizziness and headache.

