#### 4.1.4. Part 2 duration

The total duration of study participation for a participant is up to approximately 122 days, with the following sequence and duration of study periods:

- **Screening** phase: from Day -90 to Day -4 pre-quarantine admission (Historical generic screening data collected through the hVIVO Generic Screening process may be transferred to this study after the study-specific consent form has been signed by the participant).
- **Inpatient phase:** Participants will be resident in the Quarantine Unit for approximately 16 days (from Day -3 to Day +12). Procedures will include:
  - o Pre-HVC:
- Admission to Quarantine Unit on Day -3
- Study intervention I.V. dosing on Day -1
- o HVC:
- Challenge Virus inoculation on Day 0 (window 1 to 2 days post-treatment)
- Post-HVC
- Day 0 onwards and each day study assessments will be conducted as per Schedule of Activities
- Participants will be discharged from the Quarantine Unit on Day12 (or may remain longer at the Principal Investigator's discretion)
- Outpatient phase: study assessments will be conducted
  - Clinic visit for PK sample on Day 20 (±2 days)
  - Final safety follow-up visit(s): Day 28 (±3 days)

The study will be conducted by hVIVO which has extensive experience with RSV challenge studies. Numerous studies have been performed using experimental RSV infection in human participants. To date, in hVIVO's studies, over 1220 healthy participants (18 to 55 years of age) have been successfully and safely inoculated with RSV-A Memphis 37b. These studies demonstrated that adults could be infected by nasal inoculation and that experimental infection was safe. This strain has been shown to cause symptoms and virus shedding that closely match natural infection.

Administration of study intervention and challenge with RSV-A Memphis 37b will take place in hVIVO's specialised Clinical Units, either in the Quarantine Unit or Screening Clinic Units. Standard study procedures (including collection of blood, urine, and nasopharyngeal secretions for assessment of safety and efficacy) have been employed in previous studies conducted by hVIVO.

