##### **4.2.2.1 Adverse events**

Adverse events (AE) will be coded using the latest available version of the Medical Dictionary for Regulatory Activities (MedDRA) and will be classified by MedDRA Preferred Term (PT) and System Organ Class (SOC).

A Treatment Emergent Adverse Events (TEAE) will be defined as any adverse event that occurs from the time of first study treatment dose administered to the subject until last study visit, i.e. an AE that was not present prior to receiving the first dose of IMP.

Serious adverse events (SAE) are those AE that put the life of the subject at risk or that cause serious or permanent damage to the subject's health. An AE is to be recorded and reported as SAE in the event of any of the following:

- AE results in death
- AE is life-threatening (i.e. constitutes an immediate threat to the subject's life)

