#### **Adverse event tabulations:**

Tabulation of adverse events will present for each cell the following information: number of subjects with at least one occurrence of the event, corresponding percentage and number of events.

The following tables will be produced by treatment group:

- Summary table of adverse events (Statistical Table 14.3.1.1):
  - Any AE
  - Any TEAE
  - Any TEAE leading to study discontinuation
  - Any TEAE considered related to the study treatment (at least possibly related)
  - Any SAE
  - Any SAE leading to study discontinuation
  - Any SAE considered related to the study treatment
  - Death (if any)
  
- Detailed Tables:
  - TEAEs by SOC and PT (Statistical Table 14.3.1.2)
  - TEAEs by SOC, PT and severity (Statistical Table 14.3.1.3)
  - At least possibly related TEAEs by SOC, PT and severity (Statistical Table 14.3.1.4)
  - Listing of deaths (Statistical Table 14.3.2)
  - Narrative of deaths, other serious and significant adverse events (Statistical Table 14.3.3)

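### Adverse-event capture narrows at viral challenge, 1 to 2 days after infusion, but the Part 2 TEAE tables pool everything from dose to last visit

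*Protocol*

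**What the plan says.** **Timing.** Protocol 4.1.4 gives "Study intervention I.V. dosing on Day -1" and places inoculation on Day 0, allowing one to two days after treatment. Discharge is planned for Day 12 and the last visit for Day 28 ± 3 days.

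**Recording rule from challenge.** Protocol 10.3.6.2 (Challenge Virus Symptoms) says of the diary card: "Symptoms greater than Grade 0 will be expected and presumed to represent virus infection consequent to Viral Challenge". Such symptoms "will not be additionally captured as AEs unless they meet the definition of an AE, and are deemed to be clinically significant" in the investigator's opinion. A second route covers what the investigator regards as unexpected: these "symptoms post inoculation will be captured as AEs, along with all other occurrences that meet the criteria for an AE". Protocol 10.3.1 also lists typical viral diary-card symptoms among events that are not AEs. Parallel presumptions apply to upper and lower respiratory signs (8.5 and 10.3.6.2) and to pyrexia (8.7 and 10.3.6.2). None depends on confirmed infection.

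**Known side effects.** Protocol 2.3: "The most common side effect observed in adults was mild transient dizziness and headache". Headache is one of the 13 diary items in 8.13; dizziness is not.

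**Analysis.** SAP 4.2.2.1 defines a TEAE as an event occurring "from the time of first study treatment dose administered to the subject until last study visit" and assesses safety over the whole study. SAP 5.6.2 and 11.1 list Tables 14.3.1.1 to 14.3.1.4 by treatment group, with system organ class, preferred term, severity and relatedness as the breakdowns. None is by study period. The one extra cut is Table 14.3.1.1 in the laboratory-confirmed infected subgroup.

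**The concern.** A TEAE count is easiest to interpret when the same symptom is recorded in the same way throughout the window. Here a headache a few hours after infusion is an ordinary AE, while the same headache two days later is presumed viral and by default is not. A symptom that never becomes an AE also gets no causality assessment under Protocol 10.3.6.5. It therefore cannot reach Table 14.3.1.4, although frequency and severity of drug-related TEAEs is a stated Part 2 endpoint (Protocol 3.2).

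The events that are recorded after challenge mix drug and virus effects. If palivizumab works, its arm has fewer viral events, and the pooled table can then show fewer TEAEs on palivizumab even if the drug causes some. The short stretch in which participants have the drug but not the virus, with ordinary recording and a randomised placebo group, is never displayed by itself.

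**Working it through.** The plan states no figure on this point, so there is nothing to reproduce. The check has three steps.

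**1. How the TEAE window divides.** Inputs are infusion *g* days before challenge (planned 1, allowed 1 to 2), challenge on Day 0, discharge on Day 12, and last visit on Day *F* (planned 28, allowed 25 to 31), all from Protocol 4.1.4. Window length = *g* + *F*.

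| Period | Formula | Planned (*g* = 1, *F* = 28) | Range over allowed windows |
|---|---|---|---|
| Infusion to inoculation | *g*/(*g*+*F*) | 1/29 = 3.4% | 1/32 = 3.1% to 2/27 = 7.4% |
| Inoculation to discharge | 12/(*g*+*F*) | 12/29 = 41.4% | 12/33 = 36.4% to 12/26 = 46.2% |
| After discharge | (*F*−12)/(*g*+*F*) | 16/29 = 55.2% | 13/27 = 48.1% to 19/32 = 59.4% |

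An extended quarantine stay would enlarge the middle share. These are shares of time, not of events missed.

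**2. Direction of the pooled comparison.** In the filtered period, let *v* be the placebo rate of viral symptoms, *r* the relative reduction on palivizumab, *d* the rate of drug-caused symptoms, and *c* the share of symptoms recorded as AEs. Assume *c* is the same for both sources, since a blinded investigator cannot tell them apart, and that the rates add. Then

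- recorded, placebo: *c·v*
- recorded, palivizumab: *c*·[(1 − *r*)·*v* + *d*]
- difference: *c*·(*d* − *r·v*)

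The difference is negative whenever *r·v* > *d*, even with *d* > 0. A small *c* shrinks the offset from prevention, but it shrinks the drug signal by the same factor. Before inoculation there is no viral term and the ordinary recording rule applies, so the difference reflects drug effects alone.

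**3. What filtering could do to a drug signal (illustration only).** The documents give neither a side-effect rate nor a capture share, so both are assumed. With 25 treated participants, true risk *p* of drug headache starting in the filtered period and capture share *c*, the chance of at least one recorded headache AE is 1 − (1 − *p·c*)^25.

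| True risk *p* | *c* = 100% | 50% | 25% | 10% |
|---|---|---|---|---|
| 5% | 72% | 47% | 27% | 12% |
| 10% | 93% | 72% | 47% | 22% |
| 20% | 99.6% | 93% | 72% | 40% |

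The table shows only that the result depends strongly on a quantity the plan leaves to judgement. Headache is a case in point: Protocol 2.1 does not name it in its description of typical RSV illness, so one investigator could call it unexpected and another could presume it viral.

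**The case against.** The strongest reply is that the stated objective is safety in the challenge model. A randomised, blinded comparison from dose to last visit, under one recording rule in both arms, answers that question. This stands: the pooled tables are valid for that purpose and should be kept. They do not serve the drug-related TEAE endpoint well, because filtered symptoms are never assessed for causality.

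The second reply is that the data are not lost. This also stands in part:

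- Tables 14.2.5.3 and 14.2.5.4 show each symptom by timepoint and arm, but as efficacy output on the Evaluable set. That set omits dosed participants who are not challenged or do not complete quarantine. Protocol 1.1.6.2 expects no dropout between dosing and inoculation, so the difference may be small.
- Tables 14.2.11.1 to 14.2.11.8 give symptom proportions, but from the last Day 0 assessment onward (SAP 4.2.1.4), and again on the Evaluable set.
- Directed-examination signs, temperature and spirometry are tabulated by visit and arm on the safety set (SAP 5.6.5, 5.6.6 and 5.6.9). This largely covers signs and fever but not subjective symptoms.
- Listing 16.2.7 has onset dates, so a reader could rebuild most of the split. A date alone does not place a Day 0 event before or after inoculation.

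Third, causality is assessed for the drug and, where relevant, the challenge virus (Protocol 10.3.6.5). That helps only for symptoms that became AEs.

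A reader might infer more than the documents support. They do not show that most drug symptoms go unrecorded: no proportion is given, and the clinically-significant and unexpected routes are open. They do not show that the named side effects are suppressed, since dizziness stays under ordinary reporting and no onset time is given for either. Nor is the gap before challenge the only virus-free observation: Part 1 gives palivizumab without challenge and follows AEs to Day 18 ± 3 days, though in 6 participants, at 8 mg/kg only and without placebo. Finally, a return to ordinary capture after discharge is an inference from the diary ending; the rules for pyrexia and respiratory signs state no end.

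**Conclusion.** The concern holds as a gap in presentation and interpretation. Recording of diary-type symptoms, respiratory signs and fever narrows at challenge, 1 to 2 days after infusion, in both arms and regardless of infection, while the TEAE tables run across that change. About 3 to 7% of the TEAE window lies before it and is not shown separately. After it, prevention of infection can lower the palivizumab TEAE count and offset a drug-related excess. The size of that effect cannot be stated, because it depends on capture and symptom rates that the documents do not give.

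The conclusion rests on the default wording of Protocol 10.3.6.2 being followed and on the planned visit days. It does not imply a flawed randomised comparison or lost data. Given the partial mitigations and the exploratory aim, this is a low-to-moderate priority improvement that costs little.

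**What to change.** 1. Keep the overall TEAE tables. Add Tables 14.3.1.1 to 14.3.1.4 by period of onset and randomised arm, using the safety-set rule of treatment actually received: infusion to inoculation, inoculation to discharge, and after discharge. Assign Day 0 events by clock time. The protocol records AE onset times (10.3.6.2), dose times (6.4) and the exact inoculation time (6.2.2).
2. Add to the safety section a by-arm table, on the safety set, of diary symptoms that are new or worse after infusion, split at inoculation. First reconcile the Part 2 schedule, which shows diary cards before Day 0, with its note that three-times-daily assessments start on Day 0. The table needs a baseline before infusion.
3. State in the SAP that AE recording differs between periods, and clarify when the presumptions for pyrexia and respiratory signs end.
4. Label any breakdown by laboratory-confirmed infection, including the planned Table 14.3.1.1 subgroup, as descriptive only. Infection is a post-randomisation outcome that treatment is meant to change, so infected subsets of the two arms are not comparable.

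The cost is SAP wording and a few extra tables from data already collected. Counts will be small with 25 per arm, especially in the first period, so these tables should be read descriptively.

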#### **Physical Examination**

Any clinically significant change in complete physical examination findings during the study will be documented as an AE.

#### **Direct Physical Examination**

Following Viral Challenge, upper and lower respiratory symptoms (nasal discharge, otitis, pharyngitis, sinus tenderness, new wheezes, rales and rhonchi) will be expected and presumed to represent virus

infection consequent to Viral Challenge, and will not be additionally captured as AEs unless they meet the definition of an AE, and are deemed to be clinically significant (in the opinion of the Investigator) to be classed as AEs.

#### **Vital Signs**

Deterioration in a vital sign (compared to baseline) should only be reported as an AE if the deterioration fulfils the criteria for an AE. If deterioration in a vital sign is associated with clinical signs and symptoms, the sign or symptom will be reported as an AE and the associated vital sign will be considered as additional information.

## **Temperature**

Following Viral Challenge, pyrexia will be expected and presumed to represent virus infection consequent to Viral Challenge, and will not be additionally captured as an AE unless it meets the definition of an AE, and is deemed to be clinically significant (in the opinion of the Investigator) to be classed as an AE.

Following Viral Challenge all unexpected (in the opinion of the Investigator) pyrexia post inoculation will be captured as an AE, along with all other occurrences that meet the criteria for an AE.

#### **Spirometry**

A 15% drop in a spirometry value (compared to baseline) confirmed by a repeat on the same day, will be a Grade 1 (mild) AE. The PI/Investigator will use his/her clinical judgement to assign severity grades above Grade 1, based on evaluation of clinical signs and symptoms. If the repeated value has returned to normal an AE will not be raised.

#### **Laboratory Values**

Deterioration in a laboratory value (compared to baseline) should only be reported as an AE if the deterioration fulfils the criteria for an AE. If deterioration in a laboratory result is associated with clinical signs and symptoms, the sign or symptom will be reported as an AE and the associated laboratory result will be considered as additional information.

The Investigator and/or SME will judge whether abnormal laboratory values are clinically significant or not clinically significant, and record this in the source document. This entry should be signed and dated by the relevant Investigator. Laboratory abnormalities detected at screening will be considered as part of the medical history and will not be reported as AEs

Challenge Virus associated laboratory abnormalities (e.g.: elevated ALT, AST or GGT; decreased neutrophils) may be recorded as AEs (at the discretion of the Investigator).

#### **C-reactive Protein**

Any value above 5 mg/L but less than 60 mg/L will be a Grade 1 (mild) AE (unless deemed non clinically significant by the PI or delegate. The PI or delegate will use his/her clinical judgement to assign severity grades above Grade 1, based on evaluation of clinical signs and symptoms.

## 10.3.6.3. Assessment of Intensity

The term 'severe' is often used to describe the intensity (severity) of a specific event. This is not the same as 'serious' which is based on participant/event outcome or action criteria.

The PI will use the [grading scale for AEs] as a reference when collecting, reporting and clarifying database queries of AEs, SAEs and ARs.

The severity of an AE that does not appear in the [grading scale for AEs] should be determined according to the definitions in Table 7

Table 7 - Classification of Adverse Event Severity

Grade	Classification	Definition
Grade 1	Mild	Mild level of discomfort, and does not interfere with regular activities
Grade 2	Moderate	Moderate level of discomfort that intermittently interferes with regular activities
Grade 3	Severe	Significant level of discomfort and prevents regular activities

An event is defined as 'serious' when it meets at least 1 of the predefined outcomes as described in the definition of an SAE, NOT when it is rated as severe. It is important to distinguish between serious and severe AEs. An AE of severe intensity needs not necessarily be considered serious. For example, a migraine headache that incapacitates a participant for many hours may be severe, whereas a stroke that results in a limited degree of disability may be considered mild, but should be reported as a SAE.

#### 10.3.6.4. Frequency

The frequency of the AE should be categorised as one of the following:

- Single
- Intermittent
- Continuous

## 10.3.6.5. Assessment of Causality

- The Investigator is obligated to assess the relationship between study intervention and each occurrence of each AE/SAE.
- A "reasonable possibility" of a relationship conveys that there are facts, evidence, and/or arguments to suggest a causal relationship, rather than a relationship cannot be ruled out.
- The Investigator will use clinical judgment to determine the relationship.
- Alternative causes, such as underlying disease(s), concomitant therapy, and other risk factors, as
  well as the temporal relationship of the event to study intervention administration will be considered
  and investigated.

- The Investigator will also reference the Reference Safety Information (RSI) section in the SmPC, in his/her assessment.
- For each AE/SAE, the Investigator **must** document in the medical notes that he/she has reviewed the AE/SAE and has provided an assessment of causality.
- There may be situations in which an SAE has occurred and the Investigator has minimal information
  to include in the initial report to Sponsor's Pharmacovigilance provider. However, it is very important
  that the investigator always make an assessment of causality for every event before the initial
  transmission of the SAE data.
- The Investigator may change his/her opinion of causality in light of follow-up information and send a SAE follow-up report with the updated causality assessment.
- The causality assessment is one of the criteria used when determining regulatory reporting requirements.
- The relationship of an AE to the IMP will be categorised as shown in Table 8:

Table 8- Classification of Adverse Event Relationship

Classification	Definition
Not related	The AE is related to an aetiology other than the IMP (the alternative aetiology must be documented in the participant's medical record).
Unlikely to be related	The AE is unlikely to be related to the IMP and likely to be related to factors other than IMP.
Possibly related	There is an association between the AE and the administration of the IMP, and there is a plausible mechanism for the AE to be related to the IMP, but there may also be alternative aetiology, such as characteristics of the participant's clinical status or underlying disease.
Probably related	A reasonable temporal sequence of the AE and the IMP administration exists and, based upon the known pharmacological action of the drug, known or previously reported adverse reactions to the drug or class of drugs, or judgment based on the Investigator's clinical experience, the association of the AE with the IMP seems likely.
Definitely related	A definite causal relationship exists between the AE and the administration of the IMP, and other conditions do not appear to explain the AE.

Unless an AE is 'definitely related' to the IMP, a causal relationship to one of the following should be considered, and full details provided on the AE reporting form as appropriate.

- Challenge Virus
- Study procedures
- Concomitant medication
- Other

#### 10.3.6.6. Action Taken

The Investigator should ensure that adequate medical care is provided to participants for any AEs, including clinically significant laboratory values related to the IMP. In addition, the Investigator will describe whether any treatment was given for the AE.

The Investigator will classify the action taken with regard to the AE. The action taken should be classified according to the following categories and full details provided as appropriate:

- None
- Non-drug therapy given
- Concomitant medication taken
- IMP dose not changed
- IMP dose adjusted
- IMP administration temporarily interrupted
- IMP administration permanently discontinued
- Participant withdrawn
- · Participant hospitalised
- Other

#### 10.3.6.7. Outcome

An AE should be followed until the Investigator has determined and recorded the outcome or an alternative explanation. The outcome should be classified according to the categories shown in Table 9.

Table 9 - Classification of Adverse Event Outcome

Classification	Definition	
Resolved	Resolution of the AE with no residual signs or symptoms	
Resolved with sequelae	Resolution of the AE with residual signs or symptoms	
Ongoing	Either incomplete improvement or no improvement of the AE, such that it remains on-going	
Fatal	Outcome of the AE was death. 'Fatal' should be used when death was at least possibly related to the AE.	
Unknown (e.g. Lost to follow-up)	Outcome of the AE is not known (e.g. the participant is lost to follow-up).	

